#### **4.1.2 Part B**

Part B of this study is an ethnobridging study evaluating the safety, tolerability, and PK of a single oral dose of UCB0599 at 3 dose levels (90mg, 180mg, and 360mg) under normal gastric pH conditions in healthy participants of Japanese and Chinese origins. Each group of ethnic origin (N=15 total for each) will be randomized to a 4-treatment, 6-sequence, 2-period crossover study using UCB0599:placebo in a 4:1 ratio, as shown below and in the Study Schema ([Figure 1-1](#)). Sequence 6 will only commence after Sequence 5 has been completed for all 4 participants. Sequences 3 and 4 (Cohort 3) will only commence after Sequences 1 and 2 (Cohort 2) have been

completed for all 5 participants; Sequences 5 and 6 (Cohort 4) will only commence after Sequences 3 and 4 have been completed for all 5 participants allowing the SMC review to be carried out before the start of Sequence 5.

- Sequence 1: placebo 90mg, followed by placebo 180mg (N=1)
- Sequence 2: UCB0599 90mg followed by UCB0599 180mg (N=4)
- Sequence 3: placebo 180mg, followed by placebo 360mg (N=1)
- Sequence 4: UCB0599 180mg, followed by UCB0599 360mg (N=4)
- Sequence 5: placebo 360mg, followed by placebo 90mg (N=1)
- Sequence 6: UCB0599 360mg, followed by UCB0599 90mg (N=4)

See Section 3 for more details on the objectives and endpoints of the study.

No participant will ever receive both UCB0599 and placebo, and therefore no intra-participant comparison will be possible; the crossover aspect of the Part B design refers to the dose level over 2 periods in order to limit the number of participants to be recruited into this study. This design will allow the collection of UCB0599 data at each dose level for 8 study participants of each ethnic origin and the collection of dose-matching placebo data for 2 study participants of each ethnic origin for each dose. Participants will be blinded to the treatment (ie, UCB0599 or placebo), but not to the dosage within a sequence.

Part B consists of the following periods (for a total duration of up to 45 days):

- A 28-day Screening Period (2 to 28 days before administration of study medication)
- 2 treatment periods (for a total duration of up to 10 days)

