#### **9.4.2.2 Part B**

The primary objective of Part B is to evaluate the plasma PK of UCB0599 after administration of a single dose of an oral formulation in healthy participants of Japanese and Chinese origins.

The PK parameters ( $C_{max}$ ,  $AUC_{0-t}$ , and  $AUC_{inf}$ ) will be used to estimate the following:

- PK parameters for the 3 groups (Part A healthy participants, Japanese participants, and Chinese participants)
- Dose proportionality for each group, including graphical presentation

Individual concentration-time profiles will be displayed graphically on a linear-linear scale and semilogarithmic scale.

Overall geometric mean plasma concentration-time curves and corresponding 95% CIs will be displayed by group.

No formal comparison will be made.

The PK analyses will be performed on the PK data from Part B.

The plasma concentration-time profiles and PK parameters of UCB0599 will be summarized by dose level and group using descriptive statistics (number of available observations, arithmetic mean, standard deviation, geometric mean, coefficient of variation of geometric mean, median, minimum, and maximum). Values below the LLOQ will be reported with a clear sign indicating that they were below the LLOQ. Descriptive statistics of concentrations will be calculated if at least two-thirds of the individual data points are quantifiable ( $\geq LLOQ$ ).

Descriptive statistics will be executed for all PK parameters estimated by ethnicity and dose. For  $t_{max}$ , only the median, minimum, and maximum will be reported.

The PK descriptive statistics from Part A healthy participants who receive 180mg dose of the formulation used in Part B will be presented alongside.

Dose proportionality for  $C_{max}$ ,  $AUC_{0-t}$ , and  $AUC_{inf}$  will be examined for each ethnic group and for Part A healthy participants who receive a 180mg dose of the formulation used in Part B and graphically reported. Dose proportionality could be achieved by dose normalization and log-transforming  $C_{max}$  and AUC data, in which a linear regression  $C_{max}$  versus dose and AUC versus dose will be used to assess if the slope of the regression line deviates statistically significantly from zero. If the slope is not different from zero, then it can be concluded that the PK is proportional to dose.

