## **9.9 Determination of sample size**

### **9.9.1 Part A**

To assess the relative bioavailability of 2 new formulations (film-coated tablet or encapsulated tablet) to the reference formulation (capsule) under conditions of normal or elevated gastric pH with the desired power of 90%, the study was estimated to require approximately 36 completers with a maximum of 42 randomized participants. No replacements are planned.

The assessment was based on two 1-sided ratio of means tests (TOST) for a 3-treatment, 6-sequence, 3-period complete Williams' square crossover design for continuous response data with significance level of 0.05 (5%), assuming:

- a ratio of means between any of the 2 new formulations and the reference formulation under the alternative hypothesis (H1) of 1.0
- lower and upper limits of 0.8 and 1.25, respectively
- a geometric intra-participant coefficient of variation (CV) of 28.5% based on the mean estimate of the residual variance obtained from the linear mixed effect model of the log-transformed  $C_{max}$  data from the UP0078 study ( $\sigma^2=0.0782$ ), a trial with similar participants demographics (males and female aged 18 to 55), and which used a crossover design.

For more details, please refer to the UCB0599 UP0073 sample size calculation documentation form (eTMF: "UCB0599\_UP0073\_Sample\_size\_calculation\_documentation\_form.doc").

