### **9.9.2 Part B**

A formal sample size calculation has not been performed; the group sizes are based upon historical precedent and regulatory requirements.

In order to estimate PK and safety profiles in 2 ethnic groups (Japanese and Chinese origins), it is considered that a group size of at least 10 participants in each ethnicity (8 participants on active drug at each dose and 2 participants on placebo) is appropriate. Chinese Center for Drug Evaluation (CDE) guidance suggests 8 to 12 participants per dose, whereas Japanese Pharmaceuticals and Medical Devices Agency (PMDA) guidance suggests 6 participants per dose for PK studies; both suggest 2 participants on placebo.

The Asian Pacific cohort participants will be recruited from the same clinical center as the participants from Part A (based on prior recommendation, see PMDA report on Opicapone, 2020 <https://www.pmda.go.jp/files/000243472.pdf>); and therefore, the Part A cohort of healthy participants can be used for assessment alongside the Japanese and Chinese cohorts, using the Part A PK data for a formulation of choice.

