5.4.3 Part B

5.4.3.1 Analyses required for Primary Objective (on Primary PK endpoints)

Dose proportionality for C_{max} , AUC_{0-t} , and AUC_{inf} will be examined for each participant group (Table 5-3) via the power model

$$Y = \alpha + dose^{\beta}, \quad (3)$$

where α is the subject random intercept, Y is the parameter of interest, and β is the slope. The PK parameters and the dose will be logarithmically transformed prior to analysis. The power model will be estimated by regressing the log-transformed PK parameter onto the log-transformed dose.

$$\ln(Y) = \alpha + \beta * \ln(dose) \quad (4)$$

The power model will be fitted by restricted maximum likelihood (REML) using the PROC MIXED procedure in SAS, with a fixed effect term for dose level and a random effect for participant. A lack of fit test will be performed to check the linearity assumptions for appropriateness of the power model. An unstructured covariance matrix will be specified for the participant random effect. If the model fails to converge, other covariance matrices such as VC and CS may be considered.

The results of the power model will be reported after back-transformation, including the estimated dose proportionality parameter β along with corresponding 90% CI (slope ≈ 1 implies dose proportionality).

Graphical displays including observed values, regression line of the fitted values with the 90% CI will be provided for each log-transformed PK parameter vs. log-transformed dose.

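### Protocol 9.4.2.2 concludes dose proportionality from a non-significant slope with no margin. At Part B's size that rule would usually miss a 20% departure in Cmax across 90–360mg, and the SAP's different method is not recorded as a change.

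*Protocol*

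**What the plan says.** Protocol 9.4.2.2 lists dose proportionality of Cmax, AUC0-t and AUCinf, for each group, among the quantities to be estimated under the Part B primary PK objective. On method it says "Dose proportionality could be achieved by dose normalization and log-transforming" the Cmax and AUC data. A linear regression on dose then "will be used to assess if the slope of the regression line deviates statistically significantly from zero". The inference follows directly: "If the slope is not different from zero, then it can be concluded that the PK is proportional to dose". No equivalence margin and no significance level is given. The same section says "No formal comparison will be made".

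SAP 5.4.3.1, under the analyses required for the primary objective, plans something else. It fits a power model of log parameter on log dose by REML with a random participant effect and a lack-of-fit test, and reports beta with a 90% CI. Its reading of the result is "slope ≈ 1 implies dose proportionality", again without limits. SAP 6.4, the section for changes to protocol-planned analyses, reads not applicable. The SAP is based on the protocol of 02 Mar 2023. Protocol Amendment 1 (26 Oct 2023) came after the SAP and still carries the slope rule.

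On size, Protocol 9.9.2 states of Part B: "A formal sample size calculation has not been performed". By contrast, the Part A bioavailability question is sized in Protocol 9.9.1 as two one-sided tests with "lower and upper limits of 0.8 and 1.25, respectively".

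**The concern.** A non-significant slope shows only that the data did not rule out proportionality. It does not show that departures are small. Without a margin the rule rewards imprecision: the noisier or smaller the study, the more often it returns the favourable conclusion. As literally written it is also less sensitive than the data allow. Each active participant gives two dose levels, but an ordinary regression leaves between-participant variance in the error term.

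At stake is a statement, under a primary objective, that PK is dose proportional in Japanese and in Chinese participants. Protocol 4.3 says the three doses were spaced so that proportionality could be evaluated and that steady-state PK will be projected from the single-dose data. The two governing documents also give different methods and different criteria for this one question.

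**Working it through.** **Inputs from the documents**
- Active participants per origin (Protocol 4.1.2): "Sequence 2: UCB0599 90mg followed by UCB0599 180mg (N=4"), and likewise 4 on 180→360mg (Sequence 4) and 4 on 360→90mg (Sequence 6). That is 12 participants and 24 profiles, 8 per dose.
- Within-participant variance of ln Cmax (Protocol 9.9.1): 0.0782. Check: sqrt(exp(0.0782) − 1) = 28.5%, as stated.

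**Assumptions, because the documents give no figure**
- Between-participant CV 20–40%.
- Two-sided 5% test.
- Departures are total changes in dose-normalised exposure over the fourfold range, 90 to 360mg.

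**The plan's own figure.** Part A two one-sided tests, ratio 1.0, limits 0.80–1.25, SE = sqrt(2 × 0.0782/n), df = 2n − 4: power is 90.3% at n = 35 and 91.2% at n = 36. The stated 36 completers for 90% power is reproduced, so the variance is being used as the protocol uses it.

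**Precision of the slope in Part B (mixed model)**
- Within-participant information: Σ(difference in ln dose)² = 4 × [(ln 2)² + (ln 2)² + (ln 4)²] = 11.53. Dividing by 2 × 0.0782 gives 73.7.
- Between-participant information: participant mean ln doses, relative to 180mg, are −0.347, +0.347 and 0, so the sum of squares is 4 × (0.120 + 0.120) = 0.961. The variance of a participant mean is 0.0782/2 + ln(1 + CV²), which is 0.0783 at CV 20% and 0.1875 at CV 40%. The information is 12.3 and 5.1.
- SE of the slope = 1/sqrt(73.7 + 12.3) = 0.108, to 1/sqrt(73.7 + 5.1) = 0.113.
- 90% CI half-width (t with 11 df = 1.796): 0.19 to 0.20 on beta. On the 360mg/90mg dose-normalised ratio, 4^(beta−1), that is times or divided by about 1.3.

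**Chance of a non-significant slope.** A departure ratio R corresponds to a slope shift of ln R/ln 4, for example ln 0.8/ln 4 = −0.161. Mixed-model rates come from the noncentral t with 11 df. Rates for the protocol's regression on raw dose (22 df) come from simulation of this design.

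| True change, 90 to 360mg | Regression as written | Mixed-model test |
|---|---|---|
| none | 97–98% | 95% |
| −20% | 78–89% | 72–74% |
| +20% | 85–92% | 80–81% |
| +30% | 70–86% | 64–66% |
| −30% | 49–73% | 41–45% |

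The first row shows how little the written rule separates a proportional drug from one that is 20% off.

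**Sensitivity (mixed model, between-participant CV 0–60%)**
- Alpha 10%: −20% is missed in 56–63%, +20% in 66–71%, +30% in 45–54% and −30% in 23–32%.
- Within-participant CV of about 20% (an assumption, for instance for AUC), alpha 5%: +20% is missed in 62–69% and +30% in 33–45%. At a CV of about 15%: 40–51% and 11–21%.
- If the departure were 20% or 30% per doubling rather than over the whole range, alpha 5%, Cmax CV 28.5%: missed in 34–45% and 7–15%.

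**The case against.** The strongest reply is that the SAP governs the detail and contains no test of slope = 0. Protocol section 9 defers to it, and it plans a better model with a 90% CI. The protocol's method wording is permissive and the section disclaims formal comparison. On this view the SAP's remark about a slope near 1 is a gloss, not an accept/reject rule. Much of this stands: the as-written rates describe the protocol's analysis, not the SAP's. It does not remove the defect. The protocol's inference sentence is explicit, it survives in the amended protocol, and nothing in SAP 6.4 says it has been superseded. The SAP's gloss also gives the interval no role in the conclusion.

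The documents do not support several stronger readings that a reader might infer:
- *A finding of proportionality is assured whatever the truth.* A 30% fall is missed in 41–45% of trials under a mixed-model test. At an assumed within-participant CV of 20%, a true slope of 0.75 (29% below proportional at 360mg) is missed in only 17–20%.
- *The rates hold for AUC.* No AUC variance is given.
- *The choice of 360mg depends on this result.* Protocol 4.2 and 4.3 rest the doses on earlier studies and the likely therapeutic range. The interim analysis concerns formulation and the safety committee concerns safety, so no stated decision turns on Part B proportionality.
- *The Part A limits should be the acceptance criterion here.* No document applies 0.80–1.25 to a fourfold dose range, and an exactly proportional Cmax would meet those limits in only about 2–6% of trials.

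**Conclusion.** The point holds in limited form. The protocol's rule is an invalid inference. At the one variance the documents give, it would usually report proportionality for Cmax when exposure is 20% off in either direction, or 30% too high, across 90–360mg. For a 30% fall it runs from about even odds to nearly three in four as written, and below even odds with a mixed-model test. These sizes rest on an assumed between-participant CV of 20–40% and an assumed two-sided 5% level. They shrink with a 10% level or lower variability. The SAP has already moved to a sounder analysis, so what remains is an unsound sentence in the current protocol, a criterion without limits in the SAP, and an unrecorded difference between the two. It should be corrected; it does not threaten the study.

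**What to change.** 1. In Protocol 9.4.2.2, delete the slope-significance test and the sentence that concludes proportionality from it. Refer instead to the mixed power model of SAP 5.4.3.1.
2. In SAP 6.4, record the change of method from the protocol.
3. In SAP 5.4.3.1, replace the remark about a slope near 1. For each origin and each of Cmax, AUC0-t and AUCinf, report beta and the implied 360mg/90mg dose-normalised ratio 4^(beta−1), both with 90% CIs. State that no conclusion of proportionality will be drawn from p > 0.05, or from the point estimate being near 1.

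The cost is a few sentences in each document, with no added participants or samples; the 90% CI for beta is already planned. The downside is that there will be no yes/no verdict. At this size the Cmax interval is wide (beta ± about 0.19–0.20, or a ratio times or divided by about 1.3), and the report should show that width.

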#### **9.4.3 Other PK endpoint analyses**

##### **9.4.3.1 Part A**

The other PK parameters of UCB0599 and metabolites will be summarized by formulation and condition of gastric pH (elevated and normal) using descriptive statistics as described in Section 9.4.2.1.

- For UCB0599:  $t_{max}$ ,  $t_{1/2}$ , CL/F, and Vz/F (if possible but not limited). For  $t_{max}$ , only the median, minimum, and maximum will be reported.
- For **CCI** metabolites:  $C_{max}$ ,  $t_{max}$ ,  $AUC_{0-t}$ ,  $AUC_{inf}$ , and each metabolite/parent  $C_{max}$  and AUC ratio (corrected for the molecular weight of the entities), as appropriate.

##### **9.4.3.2 Part B**

The other PK parameters of UCB0599 and metabolites will be summarized by ethnicity and dose using descriptive statistics as described in Section 9.4.2.2.

- Other PK parameters of UCB0599:  $t_{max}$ , CL/F, Vz/F,  $t_{1/2}$ ,  $C_{max}/BW/D$ ,  $AUC_{0-t}/BW/D$ , and  $AUC_{inf}/BW/D$ . For  $t_{max}$ , only the median, minimum, and maximum will be reported.
- Other PK parameters of **CCI** metabolites:  $C_{max}$ ,  $t_{max}$ ,  $AUC_{0-t}$ , and  $AUC_{inf}$ , and each metabolite/parent AUC ratio, as appropriate.

### **9.5 Planned safety and other analyses**

#### **9.5.1 Safety analyses**

Unless stated otherwise, all safety analyses will be performed on the SS.

All AEs will be coded using the most recent Medical Dictionary for Regulatory Activities (MedDRA®) and characterized as pretreatment and treatment emergent according to the intake of the study medication.

The occurrence and incidence of TEAEs will be summarized by MedDRA system organ class (SOC), HLT, and preferred term (PT), and by treatment and ethnic group (for Part B only). The occurrence and incidence of TEAEs will also be summarized by maximum event intensity and by relationship to the study medication. Adverse events will be categorized by severity (mild/moderate/severe). All AEs will be listed and will include actions taken for each AE, the time of onset of the AE after dosing, and the duration of each AE. Adverse events leading to discontinuation and SAEs will also be summarized by treatment group and ethnic group.

Laboratory variables and changes from Baseline will be summarized by time point and will be presented by treatment and ethnic group. For categorized values according to the reference range, shift tables from Baseline (Day -1, or Day 1 prior to first treatment) to each post-Baseline

time point will be presented for selected variables to be defined in the SAP. Values outside the reference range will be flagged in the listings.

Vital sign variables (SBP and DBP, pulse rate, respiration rate, and body temperature) and changes from Baseline (Day -1, or Day 1 prior to first treatment) will be summarized by time point and will be presented by treatment and ethnic group.

Single 12-lead ECGs will be recorded at each time point as noted in the study Schedule of Activities (Section 1.3). Descriptive statistics will be presented for ECG values and changes from Baseline (Day -1, or Day 1 prior to first treatment) over time.

See Section 9.8 for details on planned interim analyses and data monitoring.

## **9.6 Handling of protocol deviations**

Important protocol deviations are deviations from the protocol which potentially could have a meaningful impact on study conduct, or on the PK and key safety for an individual study participant. The criteria for identifying important protocol deviations will be defined within the appropriate protocol-specific document. Important protocol deviations will be reviewed as part of the ongoing data cleaning process and all important deviations will be identified and documented to confirm exclusion from analysis sets. All important deviations will be identified and documented to confirm exclusion from the analysis sets.

## **9.7 Handling of dropouts or missing data**

In general, there will be no imputation of missing data. Handling of missing or partial dates and/or times for safety assessments will be described in the SAP.

## **9.8 Planned interim analysis and data monitoring**

There is 1 planned interim analysis. After completion of Part A, an interim analysis will be performed on key PK endpoints for all data, to support the decision on selection of the Part B formulation.

An SMC will be established before the start of the study (as described in Section 10.1.6). During Part B, data will be examined after Cohort 3, in order to proceed to the next dose level in the Japanese and Chinese participants. Throughout the study, safety and tolerability data will be reviewed on an ongoing basis by the SMC as described in Section 4.1. A detailed description of the composition and conduct of the SMC will be provided in a separate SMC Charter.

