## **6.3 Measures to minimize bias: randomization and blinding**

Part A is an open-label, randomized, 2 in-series crossover substudies, each with a fixed sequence complete block design of 3 treatment periods in healthy male and female participants. This portion of the study is planned to enroll up to 42 study participants, in which 7 participants will

be randomized (approximately 6 completers) to each sequence. Randomization numbers will be assigned at the site in an unblinded fashion and will be entered into the eCRF.

In Part B, 15 study participants of each ethnic origin will be randomized to the 4 treatments following a UCB0599:placebo 4:1 ratio (see Section 4.1 for study design details). Participants will be blinded to the treatment (ie, UCB0599 or placebo), but not to the dosage within a sequence. As study participants are being screened for Part B, participants will be randomized to blocks of 2 sequences at a time: Sequences 1 and 2 (Cohort 2), followed by Sequences 3 and 4 (Cohort 3), and finally Sequences 5 and 6 (Cohort 4) after the SMC review.

An interactive response technology (IRT) will be used for assigning eligible participants (in Part A and Part B) to a treatment regimen (as applicable) based on a predetermined production randomization and/or packaging schedule provided by UCB (or designee). The randomization schedule will be produced by the IRT vendor. The IRT will generate individual assignments for kits of the study medication, as appropriate, according to the visit schedule.

To enroll a study participant (Visit 1), the Investigator or designee will contact the IRT and provide brief details about the participant to be enrolled. Each participant will receive a 5-digit number assigned at screening that serves as the participant identifier throughout the study. The participant number will be required in all communication between the Investigator or designee and the IRT regarding a particular participant. Participant numbers and kit numbers will be tracked via the IRT.

To randomize a participant, the Investigator or designee will contact the IRT and provide brief details about the participant to be randomized. The IRT will automatically inform the investigator or designee of the participant's randomization number. The IRT will allocate kit numbers to the participant based on the participant number during the course of the study. The randomization number must be incorporated into the eCRF.

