### **7.1.5 General stopping criteria for the study - Part B only**

UCB will halt further dosing if any of the following criteria are met during the course of the study and following case review to confirm causality and seriousness and/or severity of reported events.

During the study, planned dosing and procedures must be discontinued or suspended for all remaining study participants who are yet to be dosed in the study and appropriate follow-up procedures established for (but not limited to) any of the following reasons: One study participant has an SAE considered related to the study medication as judged by the Investigator. Two or more study participants in a single cohort have a severe AE, similar clinically significant abnormal laboratory results or other clinically significant safety findings that would be unacceptable for this study population. If one of the stopping criteria for dosing and single dose escalation has been met, the SMC will meet as soon as possible to make a recommendation on discontinuation, pausing, or suspension of study medication dosing or on the stopping or continuation of the study. Consideration will be given to severity and relatedness of events. Further details on the role and process of ensuring close safety monitoring through the SMC are provided in the respective charters. See the Schedule of Activities (Section 1.3) for data to be collected at the time of treatment discontinuation and follow up. Temporary discontinuation

The Investigator or SMC may consider temporary discontinuation of dosing of study participants on a case-by-case basis (for Part B only).

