5.8 Safety Monitoring Committee (SMC)

An SMC is planned for between Cohort 3 and Cohort 4 in Part B of the study to assess the safety data accumulated. This is set to take place once all participants of one ethnic group have completed Day 10 assessments. A detailed description of the composition and conduct of the SMC will be provided in a separate SMC Charter.

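### The only scheduled safety review tied to starting a Part B cohort falls after the first 360mg doses, so it releases no new dose level, contrary to Protocol 9.8

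*Protocol*

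**What the plan says.** Protocol 9.8 gives the Part B data review a purpose: "data will be examined after Cohort 3, in order to proceed to the next dose level in the Japanese and Chinese participants". Section 7.1.5 likewise speaks of escalation: "If one of the stopping criteria for dosing and single dose escalation has been met", the SMC is to meet promptly.

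Section 4.1.2 and Table 1-2 set the doses. In each origin, Cohort 2 (Sequences 1 and 2) gives 90mg then 180mg. Cohort 3 gives 180mg then 360mg ("Sequence 4: UCB0599 180mg, followed by UCB0599 360mg (N=4" per origin). Cohort 4 reverses direction ("Sequence 6: UCB0599 360mg, followed by UCB0599 90mg (N=4" per origin). Section 4.3 names 360mg as the largest single dose in Part B.

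The scheduled review sits in one place throughout. Section 4.1.2 has "Sequences 3 and 4 have been completed for all 5 participants allowing the SMC review to be carried out before the start of Sequence 5". Section 6.3 orders randomization as "Sequences 3 and 4 (Cohort 3), and finally Sequences 5 and 6 (Cohort 4) after the SMC review". SAP 5.8 says "An SMC is planned for between Cohort 3 and Cohort 4 in Part B of the study to assess the safety data accumulated", and adds that the meeting is held when one ethnic group has finished its Day 10 assessments. The earlier step carries a completion condition only: "Sequences 3 and 4 (Cohort 3) will only commence after Sequences 1 and 2 (Cohort 2) have been" completed, with no SMC decision named.

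**The concern.** A reader of 9.8 would take the review after Cohort 3 to stand between participants and a dose level that Japanese and Chinese participants have not yet received. Under the dosing table it does not. Both upward steps, 90mg to 180mg and 180mg to 360mg, first occur on Day 6 within a cohort (Cohort 2 and Cohort 3 respectively), in participants dosed five days earlier.

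Safety and tolerability are a primary objective of Part B. Section 2.3 lists drug hypersensitivity as an important identified risk and cardiac effects as an important potential risk. Investigators, the ethics committee and the SMC need one answer to the question of which doses wait for SMC release. At present the stated purpose of the review and the order of dosing give different answers.

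**Working it through.** No power or sample-size formula applies. The check is a count over the six sequences.

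**Inputs** (Protocol 4.1.2, Table 1-2): each origin has 4 active participants in each of Sequences 2, 4 and 6, and 1 placebo participant in each of Sequences 1, 3 and 5.

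**Reproducing the plan's own figure.** Active exposures per origin:
- 90mg: Sequence 2 Period 1 (4) + Sequence 6 Period 2 (4) = 8
- 180mg: Sequence 2 Period 2 (4) + Sequence 4 Period 1 (4) = 8
- 360mg: Sequence 4 Period 2 (4) + Sequence 6 Period 1 (4) = 8

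Placebo gives 1 + 1 = 2 per dose, and the total is 3 × (4 + 1) = 15. This matches the 8 active and 2 placebo per dose stated in 4.1.2.

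**Position relative to the review, in an origin that has completed Cohort 3:**

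| Dose | First active use | Active exposures before review | After review |
|---|---|---|---|
| 90mg | Cohort 2, Period 1 | 4 of 8 | 4 |
| 180mg | Cohort 2, Period 2 | 8 of 8 | 0 |
| 360mg | Cohort 3, Period 2 | 4 of 8 | 4 |

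No dose level has its first use in Cohort 4, and 360mg is the ceiling. Both upward steps come before the review and none comes after it.

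**Range over both origins.** SAP 5.8 triggers the meeting on one ethnic group, which can only mean that group's Cohort 3 participants, since Cohort 4 has not started. The five participants counted in 4.1.2 (4 active + 1 placebo) are also one origin's cohort. No text says whether the other origin must have caught up.
- Both origins have completed Cohort 3: 360mg 4 + 4 = 8 of 16; 180mg 8 + 8 = 16 of 16.
- Only one has, and the other has received neither dose: 360mg 4 + 0 = 4 of 16; 180mg 8 + 0 = 8 of 16.

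The ranges are therefore 4 to 8 of 16 at 360mg and 8 to 16 of 16 at 180mg.

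**Other SMC reviews in the documents.** Sections 4.1.2 and 9.8 provide ongoing review, 10.1.6 allows ad hoc meetings, and 7.1.4 and 7.1.5 convene the SMC when a stopping criterion is met. None is stated as a condition for starting Cohort 3 or for giving its Day 6 dose.

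**The case against.** The strongest reply is that the review does control something real. Cohort starting doses rise from 90mg to 180mg to 360mg, and Cohort 4 is the first in which a participant receives 360mg without having first taken a lower dose. That stands, and it may be what 9.8 intends. But it is a new condition of exposure, not a new dose level, and 9.8 does not say so.

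Second, safeguards do exist before the first 360mg dose. Cohort 3 waits for Cohort 2 to finish through 180mg. Participants stay in the clinic, with laboratory tests and a physical examination on Day 5 and an ECG before the Day 6 dose (Table 1-4). Section 7.1.5 suspends dosing after one related serious event, or after severe or similar significant findings in two or more participants of a cohort; 7.1.4 does so on hypersensitivity triggers. A reader might infer that the first 360mg dose is given without SMC oversight. The documents do not support that: what is missing is a stated release decision.

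Third, a reader might infer that both origins always receive 360mg before the review, so that 8 of 16 exposures at 360mg and all 16 at 180mg precede it. Under SAP 5.8 that holds only if both have completed Cohort 3. For a slower origin the review could fall before its own 360mg doses, although no text makes those doses wait.

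Fourth, section 4.2 reports single doses of 45mg to 450mg already tested and expects no exposure difference in these populations. The documents therefore give no ground for reading this point as a claim that 360mg, or the order of doses, is unsafe.

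Finally, Figure 1-1 and the SMC charter are not available and could show further reviews. The sentence in 9.8 would still conflict with Table 1-2.

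**Conclusion.** The contradiction holds. Protocol 9.8 describes a review that allows progress to the next dose level. Under Table 1-2 and 4.1.2, an origin that has completed Cohort 3 has no higher level left. What the review releases there is 4 active exposures at 360mg, given as the participants' first dose, and 4 at 90mg.

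Before the review, 4 of 8 active 360mg and 8 of 8 active 180mg exposures have been given in each such origin. The ranges over both origins are 4 to 8 of 16 and 8 to 16 of 16; the upper ends assume that both have completed Cohort 3, the lower ends that the other has received neither dose. The statement that no other review is a condition for the first 360mg dose is limited to the documents seen.

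This is more than a slip of wording, because a stated safety rule does not do what it says. It must be reconciled, but it is not evidence that dosing is unmonitored or that a given dose is wrong.

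**What to change.** Reconcile Protocol 9.8, 4.1.2 and 7.1.5, SAP 5.8 and the SMC charter with Table 1-2, so that the review and the doses it is said to release match. Either the review comes before the dose level it is stated to release, or 9.8 names the doses that do await it. State once, and repeat consistently, whether the trigger is one origin or both, and which doses in the other origin wait for the outcome. The sponsor and SMC decide which passage governs.

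Two neighbouring conflicts belong in the same edit. Section 4.1.2 makes Sequence 6 wait for four participants in Sequence 5, which has one. It also cites 9.8 for a Part B safety interim analysis, whereas the interim analysis in 9.8 is of PK data after Part A.

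The cost is wording in the protocol, SAP and charter. If the review point moves, add a short pause for one meeting of a committee that already exists. No extra participants or procedures are needed.
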